### EPWORTH SLEEPINESS SCALE SCORE

A score of <8	indicates normal sleep function
A score of 8-10	indicates mild sleepiness
A score of 11-15	indicates moderate sleepiness
A score of 16-20	indicates severe sleepiness
A score of 21-24	indicates excessive sleepiness

### **Attachment 3: Hamilton Rating Scale for Depression (HAM-D)**

#### **1. Depressed mood (Sadness, hopeless, helpless, worthless)**

- 0 = Absent
- 1 = Gloomy attitude, pessimism, hopelessness
- 2 = Occasional weeping
- 3 = Frequent weeping
- 4 = Patient reports highlight these feelings states in his/her spontaneous verbal and non-verbal communication.

#### **2. Feelings of guilt**

- 0 = Absent
- 1 = Self-reproach, feels he/she has let people down
- 2 = Ideas of guilt or rumination over past errors or sinful deeds
- 3 = Present illness is punishment
- 4 = Hears accusatory or denunciatory voices and/or experiences threatening visual hallucinations. Delusions of guilt.

#### **3. Suicide**

- 0 = Absent
- 1 = Feels life is not worth living
- 2 = Wishes he/she were dead, or any thoughts of possible death to self
- 3 = Suicide, ideas or half-hearted attempt
- 4 = Attempts at suicide (any serious attempt rates 4)

#### **4. Insomnia, early**

- 0 = No difficulty falling asleep
- 1 = Complaints of occasional difficulty in falling asleep i.e. more than half-hour
- 2 = Complaints of nightly difficulty falling asleep

#### **5. Insomnia, middle**

- 0 = No difficulty
- 1 = Patient complains of being restless and disturbed during the night
- 2 = Walking during the night – any getting out of bed rates 2 (except voiding bladder)

#### **6. Insomnia, late**

- 0 = No difficulty
- 1 = Waking in the early hours of the morning but goes back to sleep
- 2 = Unable to fall asleep again if he/she gets out of bed

#### **7. Work and activities**

- 0 = No difficulty
- 1 = Thoughts and feelings of incapacity related to activities: work or hobbies
- 2 = Loss of interest in activity – hobbies or work – either directly reported by patient or indirectly seen in listlessness, in decisions and vacillation (feels he/she has to push self to work or activities)
- 3 = Decrease in actual time spent in activities or decrease in productivity. In hospital, rate 3 if patient does not spend at least three hours a day in activities
- 4 = Stopped working because of present illness. In hospital rate 4 if patient engages in no activities except supervised ward chores

#### **8. Retardation : Psychomotor (Slowness of thought and speech; impaired ability to concentrate; decreased motor activity)**

- 0 = Normal speech and thought
- 1 = Slight retardation at interview
- 2 = Obvious retardation at interview

- 3 = Interview difficult
- 4 = Interview impossible

### **9. Agitation**

- 0 = None
- 1 = Fidgetiness
- 2 = Playing with hands, hair, obvious restlessness
- 3 = Moving about; can't sit still
- 4 = Hand wringing, nail biting, hair pulling, biting of lips, patient is on the run

### **10. Anxiety, psychic**

Demonstrated by: subjective tension and irritability, loss of concentration, worrying about minor matters, apprehension, fears expressed without questioning, feelings of panic, feeling jumpy

- 0 = Absent
- 1 = Mild
- 2 = Moderate
- 3 = Severe
- 4 = Incapacitating

### **11. Anxiety, somatic**

Physiological concomitants of anxiety such as:

- gastrointestinal: dry mouth, wind, indigestion, diarrhea, cramps, belching
  - cardiovascular: palpitations, headaches
  - respiratory: hyperventilation, sighing
  - urinary frequency
  - sweating
  - giddiness, blurred vision
  - tinnitus
- 0 = Absent
  - 1 = Mild
  - 2 = Moderate
  - 3 = Severe
  - 4 = Incapacitating

### **12. Somatic symptoms: gastro-intestinal**

- 0 = None
- 1 = Loss of appetite but eating without encouragement from others. Food intake about normal.
- 2 = Difficulty eating without urging from others. Marked reduction of appetite and food intake.

### **13. Somatic symptoms: general**

- 0 = None
- 1 = Heaviness in limbs, back or head; backaches, headaches, muscle aches, loss of energy, fatigability
- 2 = Any clear-cut symptom rates 2

### **14. Genital Symptoms**

Symptoms such as: loss of libido, menstrual disturbances

- 0 = Absent
- 1 = Mild
- 2 = Severe

### **15. Hypochondriasis**

- 0 = Not present
- 1 = Self-absorption (bodily)
- 2 = Preoccupation with health
- 3 = Strong conviction of some bodily illness
- 4 = Hypochondrial delusions

## 16. Loss of Weight

Rate either 'A' or 'B':

### A When rating by history:

- 0 = No weight loss
- 1 = Probable weight loss associated with present illness
- 2 = Definite (according to patient) weight loss

### B Actual weight changes (weekly):

- 0 = Less than 1 lb (0.5 kg) weight loss in one week
- 1 = 1-2 lb (0.5 kg-1.0 kg) weight loss in week
- 2 = Greater than 2 lb (1 kg) weight loss in week
- 3 = Not assessed

## 17. Insight

- 0 = Acknowledges being depressed and ill
- 1 = Acknowledges illness but attributes cause to bad food, overwork, virus, need for rest, etc.
- 2 = Denies being ill at all

TOTAL SCORE: \_\_\_\_

### Attachment 4: Eating Attitudes Test (EAT)

**\*Please do not consider episodes of eating while you are asleep when answering this questionnaire\***

**Please check a response for each of the following statements:**

I . . .	Always	Usually	Often	Sometimes	Rarely	Never
1. Am terrified about being overweight.						
2. Avoid eating when I am hungry.						
3. Find myself preoccupied with food.						
4. Have gone on eating binges where I feel that I may not be able to stop.						
5. Cut my food into small pieces.						
6. Aware of the calorie content of foods that I eat.						
7. Particularly avoid food with a high carbohydrate content (i.e. bread, rice, potatoes, etc.)						
8. Feel that others would prefer if I ate more.						
9. Vomit after I have eaten.						
10. Feel extremely guilty after eating.						
11. Am preoccupied with a desire to be thinner.						
12. Think about burning up calories when I exercise.						
13. Other people think that I am too thin.						
14. Am preoccupied with the thought of having fat on my body.						

(continued on next page)

**Attachment 4: Eating Attitudes Test (EAT)  
continued**

**\*Please do not consider episodes of eating while you are asleep when  
answering this questionnaire\***

**Please check a response for each of the following statements:**

I . . .	Always	Usually	Often	Sometimes	Rarely	Never
15. Take longer than others to eat my meals.						
16. Avoid foods with sugar in them.						
17. Eat diet foods.						
18. Feel that food controls my life.						
19. Display self-control around food.						
20. Feel that others pressure me to eat.						
21. Give too much time and thought to food.						
22. Feel uncomfortable after eating sweets.						
23. Engage in dieting behavior.						
24. Like my stomach to be empty.						
25. Have the impulse to vomit after meals.						
26. Enjoy trying new rich foods.						

**Total Score \_\_\_\_\_**

## Attachment 5: Three Factor Eating Questionnaire (TFEQ)

**\*Please do not consider episodes of eating while you are asleep when answering this questionnaire\***

**Part I:** Read each of the following 36 statements carefully. If you agree with the statement or feel that it is true as applied to you; answer true by circling the appropriate letter (T). If you disagree with the statement, or feel that it is false as applied to you, answer false by circling the appropriate letter (F).

- |   |   |   |
|---|---|---|
| 1. When I smell a sizzling steak or see a juicy piece of meat, I find it very difficult to keep from eating, even if I have just finished a meal.             | T | F |
| 2. I usually eat too much at social occasions, like parties and picnics.  | T | F |
| 3. I am usually so hungry that I eat more than three times a day.   | T | F |
| 4. When I have eaten my quota of calories, I am usually good about not eating anymore.  | T | F |
| 5. Dieting is so hard for me because I just get too hungry.   | T | F |
| 6. I deliberately take small helpings as a means of controlling my weight.  | T | F |
| 7. Sometimes things just taste so good that I keep on eating even when I am no longer hungry.   | T | F |
| 8. Since I am often hungry, I sometimes wish that while I am eating, an expert would tell me that I have had enough or that I can have something more to eat. | T | F |
| 9. When I feel anxious, I find myself eating.   | T | F |
| 10. Life is too short to worry about dieting.   | T | F |
| 11. Since my weight goes up and down, I have gone on reducing diets more than once.   | T | F |
| 12. I often feel so hungry that I just have to eat something.   | T | F |
| 13. When I am with someone who is overeating, I usually overeat too.  | T | F |
| 14. I have a pretty good idea of the number of calories in common foods.  | T | F |
| 15. Sometimes when I start eating, I just can't seem to stop.   | T | F |
| 16. It is not difficult for me to leave something on my plate.  | T | F |
| 17. At certain times of the day, I get hungry because I have gotten used to eating then.  | T | F |
| 18. While on a diet, if I eat a food that is not allowed, I consciously eat less for a period of time to make up for it.                                      | T | F |
| 19. Being with someone who is eating often makes me hungry enough to eat also.  | T | F |
| 20. When I feel blue, I often overeat.  | T | F |
| 21. I enjoy eating too much to spoil it by counting calories or watching my weight.   | T | F |
| 22. When I see a real delicacy, I often get so hungry that I have to eat right away.  | T | F |
| 23. I often stop eating when I am not really full as a conscious means of limiting the amount that I eat.   | T | F |
| 24. I get so hungry that my stomach often seems like a bottomless pit.  | T | F |
| 25. My weight has hardly changed at all in the last ten years.  | T | F |
| 26. I am always hungry so it is hard for me to stop eating before I finish the food on my plate.  | T | F |
| 27. When I feel lonely, I console myself by eating.   | T | F |
| 28. I consciously hold back at meals in order not to gain weight.   | T | F |
| 29. I sometimes get very hungry late in the evening or at night.  | T | F |
| 30. I eat anything I want, any time I want.   | T | F |
| 31. Without even thinking about it, I take a long time to eat.  | T | F |
| 32. I count calories as a conscious means of controlling my weight.   | T | F |
| 33. I do not eat some foods because they make me fat.   | T | F |
| 34. I am always hungry enough to eat at any time.   | T | F |
| 35. I pay a great deal of attention to changes in my figure.  | T | F |
| 36. While on a diet, if I eat a food that is not allowed, I often then splurge and eat  | T | F |

other high calorie foods.

**Part II.** Each question in this section is followed by a number of answer options. After reading each question carefully, choose the one option which most applies to you and circle the appropriate number.

37. How often are you dieting in an conscious effort to control your weight?	1 Rarely	2 Sometime s	3 Usually	4 Always
38. Would a weight fluctuation of 5 lbs. affect the way you live your life?	1 Not at all	2 Slightly	3 Moderatel y	4 Very Much
39. How often do you feel hungry?	1 Only at meal times	2 Sometime s between meals	3 Often between meals	1 Almost always
40. Do your feelings of guilt about overeating help you to control your food intake?	1 Never	2 Rarely	3 Often	4 Always
41. How difficult would it be for you to stop eating halfway through dinner and not eat for the next four hours?	1 Easy	2 Slightly difficult	3 Moderatel y difficult	4 Very Difficult
42. How conscious are you of what you are eating?	1 Not at all	2 Slightly	3 Moderately	4 Very Much
43. How frequently do you avoid “stocking up” on tempting foods?	1 Almost never	2 Seldom	3 Usually	4 Almost Always
44. How likely are you to shop for low calorie foods?	1 Unlikely	2 Slightly likely	3 Moderatel y likely	4 Very likely
45. Do you eat sensibly in front of other and splurge alone?	1 Never	2 Rarely	3 Often	4 Always
46. How likely are you to consciously eat slowly in order to cut down on how much you eat?	1 Unlikely	2 Slightly likely	3 Moderately likely	4 Very likely
47. How frequently do you skip dessert because you are no longer hungry?	1 Almost never	2 Seldom	3 At least once a week	4 Almost every day
48. How likely are you to consciously eat less than you want?	1 Unlikely	2 Slightly likely	3 Moderatel y likely	4 Very likely
49. Do you go on eating binges even though you are not hungry?	1 Never	2 Rarely	3 Sometimes	4 At least once a week
50. To what extent does this statement describe your eating behavior? “I start dieting in the morning, but because of any number of things that happen during the day, by evening I have given up and eat what I want, promising myself to start dieting again tomorrow.”	1 Not like me	2 Little like me	3 Pretty good descriptio n of me	4 Describe s me perfectly

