#### Visit 1\* (Day -14)

1. Review inclusion/exclusion criteria
2. Assess concomitant medications
3. Obtain weight
4. Obtain non-fasting clinical laboratory tests as follows:
  - Urine Drug Screen [cocaine, amphetamines, methamphetamines, benzodiazepines, tetrahydrocannabinol (THC), and opiates].
  - Hemoglobin A1C
  - Creatinine (creatinine clearance will be calculated using standard formula)
5. Perform urine pregnancy test (subjects of childbearing potential only)
6. Administer the Three Factor Eating Questionnaire (TFEQ)
7. Administer the Sheehan Disability Scale
8. Dispense sleep and night eating diary
9. Record adverse events
10. Schedule return visit

\*Visits 1A and 1 may be combined for subjects who do not require washout from prohibited medications.

Subjects who are eligible for study entry based on the results of the above will be instructed to return for Visit 2 (Day 1).

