### **Efficacy Analyses**

The efficacy analyses will be performed on an intent-to-treat (ITT) population defined as all randomized subjects who were dispensed study medication and for whom one post-baseline efficacy measurement is available.

Efficacy analyses will be conducted separately for subjects with night eating syndrome or sleep-related eating disorder, and across all subjects with either of these two diagnoses. The primary efficacy parameter will be the change in the number of nights per week of the specified nocturnal eating episode.

The primary efficacy parameter of number of nights per week with nocturnal episodes will be analyzed using ANCOVA with baseline frequency of nocturnal episodes as a co-variate. Diagnostic procedures will be conducted to determine whether the statistical assumptions are met.

The MOS, SDS, TFEQ, HAM-D, HbA1C, body weight and Epworth Sleepiness Scale will be analyzed using an ANCOVA with the baseline value as a covariate.

Information obtained from the sleep diaries will be summarized.

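### TFEQ item 39 prints code 1 for both its lowest and its highest hunger answer; if the printed digit is keyed, the two cannot be told apart (minor)

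*Combined protocol and SAP*

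**What the plan says.** Attachment 5 reproduces the TFEQ. In Part II (items 37 to 50) the respondent is told to "choose the one option which most applies to you and circle the appropriate number". Item 39, "39. How often do you feel hungry", offers four answers in rising order of hunger. The first is "1 Only at meal times", the third is "3 Often between meals" and the fourth is "1 Almost always"; the second carries code 2. Item 43, in the same table, has a nearly identical fourth label and prints it as "4 Almost Always".

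The TFEQ is administered at Visit 1 (Day -14) and Visit 8 (Day 91). Under Statistical Methods, Efficacy Analyses, it is one of the listed measures that "will be analyzed using an ANCOVA with the baseline value as a covariate". No TFEQ scoring key, subscale definition or data-entry rule appears in that section or in the attachment.

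**The concern.** Part II asks for a circled number, so the digit is the natural thing to enter in a database. On item 39 two opposite answers share a digit. Once only the digit is kept, nobody working from the database can tell a subject who is hungry only at meals from one who is hungry almost all the time, and the codes drop from 3 to 1 at the top of the scale. Because the TFEQ is analysed as an outcome with its own baseline as covariate, the fault could enter both sides of that model. Nothing in the documents prevents this, and nothing in them says it will happen.

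**Working it through.** **Inputs.** Printed codes for item 39, from least to most hungry: 1, 2, 3, 1 (Attachment 5, Part II). Codes on the other Part II items: 1, 2, 3, 4. Part II holds 50 - 37 + 1 = 14 items, so 13 serve as comparators. Part III ends at item 51, so the instrument has 51 items.

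**Are the printed codes usable as an ordered score?** They give three distinct values for four ordered answers and do not rise throughout, since the last step goes from 3 to 1. Their Pearson correlation with answer order is 0.13. With the fourth code set to 4 there are four distinct values, strictly increasing.

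**Effect on one subject's change, if the printed digit is the score.** Change = Visit 8 code - Visit 1 code.

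| Move between answers | Printed codes | Codes 1 to 4 | Error |
|---|---|---|---|
| fourth to third | 3 - 1 = +2 | 3 - 4 = -1 | +3 |
| fourth to second | 2 - 1 = +1 | 2 - 4 = -2 | +3 |
| fourth to first | 1 - 1 = 0 | 1 - 4 = -3 | +3 |
| third to fourth | 1 - 3 = -2 | 4 - 3 = +1 | -3 |
| second to fourth | 1 - 2 = -1 | 4 - 2 = +2 | -3 |
| first to fourth | 1 - 1 = 0 | 4 - 1 = +3 | -3 |

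Moves that do not involve the fourth answer are recorded correctly. A subject who gives the fourth answer at both visits has the right change (0) but the wrong level.

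**Effect on a group mean, on the same condition.** Each fourth answer is recorded 1 - 4 = -3 points off. If a share p of an arm gives that answer, the bias in the arm's item mean is -3 × p. The documents give no value of p. Assumed values show the range:

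- p = 0.10: -0.30
- p = 0.25: -0.75
- p = 0.50: -1.50

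**Effect on the comparison of arms, on the same condition.** At Visit 8 the bias in topiramate minus placebo is -3 × (p_T - p_P).

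- p_T = 0.05, p_P = 0.20 (assumed): -3 × (-0.15) = +0.45
- shares reversed: -3 × (+0.15) = -0.45
- equal shares: 0

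The same error sits in the baseline covariate. Randomisation balances it on average, but not necessarily in a trial that aims for 40 subjects.

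**If position or label is scored,** every error above is 0.

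**The case against.** The strongest reply is that the documents never say the printed digit is the score. The instruction governs how the subject answers, not how the answer is entered. The TFEQ could not be scored from printed digits alone in any case: items 1 to 36 are true/false with no number, items 37 to 50 use four codes and item 51 uses six. Some statements also point in opposite directions, such as item 15 on being unable to stop eating and item 16 on finding it easy to leave food. A key outside the form is therefore needed, and how it treats item 39 is not shown. On paper the four cells differ in place and wording, so a circle round the last one is unambiguous. All of this stands, and it makes the consequence conditional. It does not remove the duplicate code from the form or guarantee that data entry will avoid it.

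A second reply is that the point rests on one character in a table extracted from PDF, where several words are visibly split. A misread 4 cannot be excluded. The 4 is read correctly in all 13 sibling items, which makes a misread less likely, but the original form should be checked first.

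A reader might also infer that the error works against topiramate, because the drug can suppress appetite. The documents do not support that. Medication Side Effects lists anorexia as a dose-related adverse event above 200 mg per day, not as an expected efficacy effect, and subjects may remain at a lower minimum effective dose. Attachment 5 also tells subjects to disregard eating while asleep, so the item does not measure the target symptom. Both arms use the same form, and any distortion depends on the share giving the fourth answer in each arm, which is unknown.

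**Conclusion.** As supplied, item 39 prints code 1 on both its first and its last answer, while every other Part II item runs from 1 to 4. This is a defect in the collection form for an analysed outcome. If the digit is keyed as printed, the two extremes merge, and any change into or out of the highest answer is wrong by 3 points on an item meant to span 1 to 4. If position or label is scored, there is no error.

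A reader might conclude that the trial scores its hungriest subjects as its least hungry. That goes too far, because no scoring rule is given. The effect on any analysed TFEQ result cannot be sized, since neither the share choosing the fourth answer nor the scoring key is stated. The scope is one of 51 items in a non-primary measure of a pilot study. The primary parameter, nights per week with nocturnal eating, is untouched. Severity is minor. The conclusion assumes that the extracted text matches the original form.

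**What to change.** Check item 39 on the original form. If the duplicate is confirmed, change the code on the fourth answer to 4. On forms already completed, enter item 39 from the position or label of the circled answer, not from the printed digit. If only digits were keyed, return to the paper for every item 39 recorded as 1. It would also help to state in Efficacy Analyses which TFEQ key and scores are used, so that the handling of this item is on record.

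The cost is a one-character correction, one data-entry instruction and a look at one item on each completed form, at most two forms per randomised subject who completes both visits. Design, sample size and the primary analysis do not change.

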**Part III:**

51. On a scale of 1 to 6, where 1 means no restraint in eating (eat whatever you want, whenever you want it) and 6 means total restraint (constantly limiting food intake and never “giving in”), what number would you give yourself?

1. eat whatever you want, whenever you want it
2. usually eat whatever you want, whenever you want it
3. often eat whatever you want, whenever you want it
4. often limit food intake, but often “give in”
5. usually limit food intake, rarely “give in”
6. constantly limiting food intake, never “giving in”

[figure not shown]

**Attachment 6:  
Sheehan Disability Scale (SDS)**

Instructions: Please mark ONE box for each scale based on your symptoms over the past week.

[figure not shown]
**WORK / SCHOOL**

The symptoms have disrupted your work / school work:

[figure not shown]
**SOCIAL LIFE**

The symptoms have disrupted your social life:

**FAMILY LIFE / HOME RESPONSIBILITIES**

The symptoms have disrupted your family life/home responsibilities:

**Please answer the following questions about how much your symptoms of Sleep-Related Eating Disorder affect you emotionally.**

1. How worried or distressed are you by your symptoms of Sleep-Related Eating Disorder?  
(circle one number)

Not Worried											Very Worried
0	1	2	3	4	5	6	7	8	9	10	

2. How ashamed are you of your symptoms of Sleep-Related Eating Disorder?  
(circle one number)

Not Ashamed											Very Ashamed
0	1	2	3	4	5	6	7	8	9	10
